5.6 Rescue Medications & Supportive Care

5.6.1 Supportive Care Guidelines

Subjects should receive appropriate supportive care measures as deemed necessary by the treating investigator. Suggested supportive care measures for the management of adverse events with potential immunologic etiology are outlined below. Where appropriate, these guidelines include the use of oral or intravenous treatment with corticosteroids as well as additional anti-inflammatory agents if symptoms do not improve with administration of corticosteroids. Note that several courses of steroid tapering may be necessary as symptoms may worsen when the steroid dose is decreased. For each disorder, attempts should be made to rule out other causes such as metastatic disease or bacterial or viral infection, which might require additional supportive care. The treatment guidelines are intended to be applied when the investigator determines the events to be related to pembrolizumab.

Note: if after the evaluation the event is determined not to be related, the investigator does not need to follow the treatment guidance (as outlined below). Refer to Section 5.2.1 for dose modification.

It may be necessary to perform conditional procedures such as bronchoscopy, endoscopy, or skin photography as part of evaluation of the event.

- **Pneumonitis:**

- For **Grade 2 events**, treat with systemic corticosteroids. When symptoms improve to Grade 1 or less, steroid taper should be started and continued over no less than 4 weeks.
- For **Grade 3-4 events**, immediately treat with intravenous steroids. Administer additional anti-inflammatory measures, as needed.
- Add prophylactic antibiotics for opportunistic infections in the case of prolonged steroid administration.

- **Diarrhea/Colitis:**

Subjects should be carefully monitored for signs and symptoms of enterocolitis (such as diarrhea, abdominal pain, blood or mucus in stool, with or without fever) and of bowel perforation (such as peritoneal signs and ileus).

- All subjects who experience diarrhea/colitis should be advised to drink liberal quantities of clear fluids. If sufficient oral fluid intake is not feasible, fluid and electrolytes should be substituted via IV infusion. For Grade 2 or higher diarrhea, consider GI consultation and endoscopy to confirm or rule out colitis.
- For **Grade 2 diarrhea/colitis** that persists greater than 3 days, administer oral corticosteroids.
- For **Grade 3 or 4 diarrhea/colitis** that persists > 1 week, treat with intravenous steroids followed by high dose oral steroids.
- When symptoms improve to Grade 1 or less, steroid taper should be started and continued over no less than 4 weeks.
- **Type 1 diabetes mellitus (if new onset, including diabetic ketoacidosis [DKA]) or \geq Grade 3 Hyperglycemia, if associated with ketosis (ketonuria) or metabolic acidosis (DKA)**
 - For **T1DM or Grade 3-4 Hyperglycemia**
 - Insulin replacement therapy is recommended for Type I diabetes mellitus and for Grade 3-4 hyperglycemia associated with metabolic acidosis or ketonuria.
 - Evaluate patients with serum glucose and a metabolic panel, urine ketones, glycosylated hemoglobin, and C-peptide.
- **Hypophysitis:**
 - For **Grade 2 events**, treat with corticosteroids. When symptoms improve to Grade 1 or less, steroid taper should be started and continued over no less than 4 weeks. Replacement of appropriate hormones may be required as the steroid dose is tapered.

- For **Grade 3-4** events, treat with an initial dose of IV corticosteroids followed by oral corticosteroids. When symptoms improve to Grade 1 or less, steroid taper should be started and continued over no less than 4 weeks. Replacement of appropriate hormones may be required as the steroid dose is tapered.

- **Hyperthyroidism or Hypothyroidism:**

Thyroid disorders can occur at any time during treatment. Monitor patients for changes in thyroid function (at the start of treatment, periodically during treatment, and as indicated based on clinical evaluation) and for clinical signs and symptoms of thyroid disorders.

- **Grade 2** hyperthyroidism events (and **Grade 2-4** hypothyroidism):
 - In hyperthyroidism, non-selective beta-blockers (e.g. propranolol) are suggested as initial therapy.
 - In hypothyroidism, thyroid hormone replacement therapy, with levothyroxine or liothyroinine, is indicated per standard of care.
- **Grade 3-4** hyperthyroidism
 - Treat with an initial dose of IV corticosteroid followed by oral corticosteroids. When symptoms improve to Grade 1 or less, steroid taper should be started and continued over no less than 4 weeks. Replacement of appropriate hormones may be required as the steroid dose is tapered.

- **Hepatic:**

- For **Grade 2** events, monitor liver function tests more frequently until returned to baseline values (consider weekly).
 - Treat with IV or oral corticosteroids
- For **Grade 3-4** events, treat with intravenous corticosteroids for 24 to 48 hours.
- When symptoms improve to Grade 1 or less, a steroid taper should be started and continued over no less than 4 weeks.

- **Renal Failure or Nephritis:**

- For **Grade 2** events, treat with corticosteroids.
- For **Grade 3-4** events, treat with systemic corticosteroids.
- When symptoms improve to Grade 1 or less, steroid taper should be started and continued over no less than 4 weeks.

- **Management of Infusion Reactions:** Signs and symptoms usually develop during or shortly after drug infusion and generally resolve completely within 24 hours of completion of infusion.

Table below shows treatment guidelines for subjects who experience an infusion reaction associated with administration of pembrolizumab (MK-3475).

Table 5 Infusion Reaction Treatment Guidelines

NCI CTCAE Grade	Treatment	Premedication at subsequent dosing
Grade 1 Mild reaction; infusion interruption not indicated; intervention not indicated	Increase monitoring of vital signs as medically indicated until the subject is deemed medically stable in the opinion of the investigator.	None
Grade 2 Requires infusion interruption but responds promptly to symptomatic treatment (e.g., antihistamines, NSAIDS, narcotics, IV fluids); prophylactic medications indicated for <=24 hrs	
Stop Infusion and monitor symptoms. Additional appropriate medical therapy may include but is not limited to:
 
 IV fluids Antihistamines NSAIDS Acetaminophen Narcotics 
Increase monitoring of vital signs as medically indicated until the subject is deemed medically stable in the opinion of the investigator. If symptoms resolve within one hour of stopping drug infusion, the infusion may be restarted at 50% of the original infusion rate (e.g., from 100 mL/hr to 50 mL/hr). Otherwise dosing will be held until symptoms resolve and the subject should be premedicated for the next scheduled dose.
 
Subjects who develop Grade 2 toxicity despite adequate premedication should be permanently discontinued from further trial treatment administration.
	
Subject may be premedicated 1.5h (\pm 30 minutes) prior to infusion of pembrolizumab (MK-3475) with:
 
Diphenhydramine 50 mg po (or equivalent dose of antihistamine).
 
Acetaminophen 500-1000 mg po (or equivalent dose of antipyretic).

Grades 3 or 4	
Stop Infusion. Additional appropriate medical therapy may include but is not limited to:
 
 IV fluids Antihistamines NSAIDS Acetaminophen Narcotics Oxygen Pressors Corticosteroids Epinephrine 
Increase monitoring of vital signs as medically indicated until the subject is deemed medically stable in the opinion of the investigator. Hospitalization may be indicated.
 
Subject is permanently discontinued from further trial treatment administration.
	No subsequent dosing
Appropriate resuscitation equipment should be available in the room and a physician readily available during the period of drug administration.		

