7.3.4 Evaluating Adverse Events

An investigator who is a qualified physician will evaluate all adverse events according to the NCI Common Terminology for Adverse Events (CTCAE), version 4.0. Any adverse event which changes CTCAE grade over the course of a given episode will have each change of grade recorded on the adverse event case report forms/worksheets.

All adverse events regardless of CTCAE grade must also be evaluated for seriousness.

Table 8 Evaluating Adverse Events

An investigator, who is a qualified physician, will evaluate all adverse events as to:

V4.0 CTCAE Grading	Grade 1	Mild; asymptomatic or mild symptoms; clinical or diagnostic observations only; intervention not indicated.
	Grade 2	Moderate; minimal, local or noninvasive intervention indicated; limiting age-appropriate instrumental ADL.
	Grade 3	Severe or medically significant but not immediately life-threatening; hospitalization or prolongation of hospitalization indicated; disabling; limiting self-care ADL.
	Grade 4	Life threatening consequences; urgent intervention indicated.
	Grade 5	Death related to AE
Seriousness	A serious adverse event is any adverse event occurring at any dose or during any use of Merck product that:	
	† Results in death; or	
	† Is life threatening; or places the subject, in the view of the investigator, at immediate risk of death from the event as it occurred (Note: This does not include an adverse event that, had it occurred in a more severe form, might have caused death.); or	
	† Results in a persistent or significant disability/incapacity (substantial disruption of one's ability to conduct normal life functions); or	
	† Results in or prolongs an existing inpatient hospitalization (hospitalization is defined as an inpatient admission, regardless of length of stay, even if the hospitalization is a precautionary measure for continued observation. (Note: Hospitalization for an elective procedure to treat a pre-existing condition that has not worsened is not a serious adverse event. A pre-existing condition is a clinical condition that is diagnosed prior to the use of a Merck product and is documented in the patient's medical history.); or	
	† Is a congenital anomaly/birth defect (in offspring of subject taking the product regardless of time to diagnosis); or	

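### For pembrolizumab-related diarrhea/colitis, Section 5.6.1 suggests starting steroids 4 days later at Grade 3-4 than at Grade 2

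*Combined protocol and SAP*

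**What the plan says.** Section 5.6.1 gives supportive-care guidance, by disorder and grade, for adverse events that the investigator attributes to pembrolizumab. Section 5.2.1.2.1 on pembrolizumab dose modification sends investigators to Section 5.6 for corticosteroid use, so this is where the protocol places its steroid guidance.

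Under Diarrhea/Colitis there are two steroid lines:

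- Grade 2: an event "that persists greater than 3 days, administer oral corticosteroids".
- Grade 3 or 4: an event "that persists > 1 week, treat with intravenous steroids followed by high dose oral steroids".

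Other measures carry no waiting period. Section 5.6.1 advises fluids and monitoring for bowel perforation, with GI consultation and endoscopy to be considered from Grade 2 upward. Table 4 holds pembrolizumab for Grade 2-3 diarrhea/colitis and stops it permanently at Grade 4. Section 5.5.2 exempts steroids given for an event of suspected immunologic origin from the ban on systemic glucocorticoids.

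**The concern.** The protocol gives the more severe event the stronger regimen (intravenous, then high-dose oral) but starts it later. A patient who presents with Grade 3 or 4 immune-related colitis would, on a literal reading, wait more than a week for steroids, while a Grade 2 patient would start after 3 days. No other text in the protocol sets an earlier steroid start for Grade 3-4 colitis.

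What is at stake is patient safety, not inference. Section 5.6.1 itself names bowel perforation as something to watch for in these patients. An investigator who relies on the written line could delay treatment in the sicker patient.

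**Working it through.** No statistical calculation applies. The check sets the thresholds against each other and then against the other lines of the same section.

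**Step 1: the two colitis thresholds.**

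- Grade 2 trigger (Section 5.6.1): more than 3 days.
- Grade 3-4 trigger (Section 5.6.1): more than 1 week = more than 7 days.
- Difference: 7 − 3 = 4 days later for the more severe grade.

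**Step 2: every Grade 3-4 steroid line in Section 5.6.1.**

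| Disorder | Grade 3-4 steroid guidance | Waiting period |
|---|---|---|
| Pneumonitis | "immediately treat with intravenous steroids" | None |
| Diarrhea/colitis | "that persists > 1 week, treat with intravenous steroids followed by high dose oral steroids" | More than 7 days |
| Hypophysitis | "treat with an initial dose of IV corticosteroids followed by oral corticosteroids" | None |
| Hyperthyroidism | "Treat with an initial dose of IV corticosteroid followed by oral corticosteroids" | None |
| Hepatic | "treat with intravenous corticosteroids for 24 to 48 hours" | None |
| Renal failure/nephritis | "events, treat with systemic corticosteroids" | None |

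The hours in the hepatic line are the length of intravenous treatment, not a delay. The Type 1 diabetes/hyperglycemia item recommends insulin and has no steroid line. Table 5 (infusion reactions) lists corticosteroids only as one option and is not counted; it states no wait either.

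Count: 6 lines, of which 1 (colitis) has a wait; 0 of the other 5 do.

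**Step 3: is the line overridden elsewhere?** Table 4 governs pembrolizumab dosing, not when steroids start. Section 5.5.2 permits steroids but sets no start time. The Grade 2 colitis line is specific to Grade 2 and does not extend to higher grades. None of these supplies an earlier start.

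**Step 4: consistency with the grading scale.** Table 8 in Section 7.3.4 describes Grade 4 as "Life threatening consequences; urgent intervention indicated". That descriptor does not prescribe steroids, but a wait of more than a week fits poorly with it.

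**The case against.** The strongest case on the other side has five parts.

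1. **The text is advisory.** Section 5.6.1 presents suggested measures, given as the treating investigator sees fit. Earlier steroids are not forbidden, and the DSMC reviews toxicity in every treated subject (Section 10.3). This stands as a limit on harm. It does not make the line correct, since the section also says the guidelines are meant to be used once an event is attributed to pembrolizumab.

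2. **Not every Grade 3-4 event waits longer.** An event that has been Grade 2 for more than 3 days before worsening would already be on oral steroids. This stands and narrows the scope: the later trigger bites on events that are Grade 3-4 at onset or reach that grade within about 3 days. Also, 4 days is the gap between two minimum durations, not a measured treatment delay.

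3. **The regimens differ.** Oral steroids at day 3 and intravenous steroids at day 7 could be read as stepwise escalation. But the Grade 2 line does not say it also covers higher grades, so a patient who presents at Grade 3 or 4 has no first step.

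4. **Colitis is handled differently throughout.** It is the only disorder in Section 5.6.1 with a persistence condition at any grade, so the comparison with the other five lines is supporting evidence only. Likewise, the Table 8 wording is a grading descriptor and covers only Grade 4. Both points are fair. The core of the concern is the order of the two thresholds within colitis, which needs neither.

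5. **A wait might help separate chemotherapy diarrhea from immune colitis.** The documents give no such reason. The guidance applies only after attribution to pembrolizumab, and any attribution argument would apply equally to Grade 2, where the wait is 3 days. It would also not fit the 14 post-operative cycles planned as pembrolizumab alone (Section 7.2.5.2.3), to which the same line applies.

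**Conclusion.** The concern holds. As written, the suggested steroid start for pembrolizumab-related Grade 3-4 diarrhea/colitis is 4 days later than for Grade 2, and it is the only one of six Grade 3-4 steroid lines in Section 5.6.1 with a waiting period. This rests on a literal, grade-specific reading of the two colitis lines, and it matters mainly for events that are severe from onset or soon after.

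Investigator discretion and the measures that apply at once reduce the likely harm but leave the guidance uncorrected. The number of patients affected cannot be estimated, because the documents give no expected colitis rate. The pCR decision rule, the sample size and the planned safety summaries are not touched. The point should be corrected as a matter of patient safety.

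**What to change.** Amend the Grade 3 or 4 diarrhea/colitis line in Section 5.6.1 so that steroids start no later than the Grade 2 trigger of more than 3 days. The simplest edit is to delete the one-week persistence condition and leave the rest of the line as it is, which would match the form of the other Grade 3-4 lines.

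The internal inconsistency alone supports a start no later than the Grade 2 trigger. Whether to go further and remove the wait entirely is a clinical decision, so the sponsor's clinicians should confirm the exact timing.

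The cost is a short clarification to one line, reissued to all four sites listed in the synopsis. Sample size, endpoints and analysis do not change.

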5.6.2 Supportive Care Guidelines for Chemotherapy Agents

Pre-infusion supportive care is permitted including administration of corticosteroids per NCCN or institutional guidelines.

Please refer to the product label or local standards of care for additional supportive measures for all chemotherapy agents (oxaliplatin, capecitabine, epirubicin).

5.7 Diet/Activity/Other Considerations

5.7.1 Diet

Subjects should maintain a normal diet unless modifications are required to manage an AE such as diarrhea, nausea or vomiting.

5.7.2 Contraception

Pembrolizumab may have adverse effects on a fetus in utero. Furthermore, it is not known if pembrolizumab has transient adverse effects on the composition of sperm.

For this trial, male subjects will be considered to be of non-reproductive potential if they have azoospermia (whether due to having had a vasectomy or due to an underlying medical condition).

Female subjects will be considered of non-reproductive potential if they are either:

- (1) postmenopausal (defined as at least 12 months with no menses without an alternative medical cause; in women <45 years of age a high follicle stimulating hormone (FSH) level in the postmenopausal range may be used to confirm a post-menopausal state in women not using hormonal contraception or hormonal replacement therapy. In the absence of 12 months of amenorrhea, a single FSH measurement is insufficient.);

OR

- (2) have had a hysterectomy and/or bilateral oophorectomy, bilateral salpingectomy or bilateral tubal ligation/occlusion, at least 6 weeks prior to screening;

OR

- (3) has a congenital or acquired condition that prevents childbearing.

Female and male subjects of reproductive potential must agree to avoid becoming pregnant or impregnating a partner, respectively, while receiving study drug and for 120 days after the last dose of study drug by complying with one of the following:

- (1) practice abstinence[†] from heterosexual activity;

OR

- (2) use (or have their partner use) acceptable contraception during heterosexual activity.

Acceptable methods of contraception are[‡]:

Single method (one of the following is acceptable):

- intrauterine device (IUD)
- vasectomy of a female subject's male partner
- contraceptive rod implanted into the skin

Combination method (requires use of two of the following):

- diaphragm with spermicide (cannot be used in conjunction with cervical cap/spermicide)
- cervical cap with spermicide (nulliparous women only)
- contraceptive sponge (nulliparous women only)
- male condom or female condom (cannot be used together)
- hormonal contraceptive: oral contraceptive pill (estrogen/progestin pill or progestin-only pill), contraceptive skin patch, vaginal contraceptive ring, or subcutaneous contraceptive injection

†Abstinence (relative to heterosexual activity) can be used as the sole method of contraception if it is consistently employed as the subject's preferred and usual lifestyle and if considered acceptable by local regulatory agencies and ERCs/IRBs. Periodic abstinence (e.g., calendar, ovulation, sympto-thermal, post-ovulation methods, etc.) and withdrawal are not acceptable methods of contraception.

‡If a contraceptive method listed above is restricted by local regulations/guidelines, then it does not qualify as an acceptable method of contraception for subjects participating at sites in this country/region.

Subjects should be informed that taking the study medication may involve unknown risks to the fetus (unborn baby) if pregnancy were to occur during the study. In order to participate in the study subjects of childbearing potential must adhere to the contraception requirement (described above) from the day of study medication initiation (or 14 days prior to the initiation of study medication for oral contraception) throughout the study period up to 120 days after the last dose of trial therapy. If there is any question that a subject of childbearing potential will not reliably comply with the requirements for contraception, that subject should not be entered into the study.

5.7.3 Use in Pregnancy

If a subject inadvertently becomes pregnant while on treatment with pembrolizumab, the subject will immediately be removed from the study. The site will contact the subject at least monthly and document the subject's status until the pregnancy has been completed or terminated. The outcome of the pregnancy will be reported to the Sponsor-Investigator and to Merck without delay and within 24 hours to the Sponsor-Investigator and within 2 working

days to Merck if the outcome is a serious adverse experience (e.g., death, abortion, congenital anomaly, or other disabling or life-threatening complication to the mother or newborn).

The study investigator will make every effort to obtain permission to follow the outcome of the pregnancy and report the condition of the fetus or newborn to the Sponsor. If a male subject impregnates his female partner the study personnel at the site must be informed immediately and the pregnancy reported to the Sponsor-Investigator and to Merck and followed as described above and in Section 7.2.2.

5.7.4 Use in Nursing Women

It is unknown whether pembrolizumab is excreted in human milk. Since many drugs are excreted in human milk, and because of the potential for serious adverse reactions in the nursing infant, subjects who are breast-feeding are not eligible for enrollment.

5.7.4.1 Pembrolizumab

It is unknown whether pembrolizumab is excreted in human milk.

5.7.4.2 Oxaliplatin

It is unknown whether oxaliplatin is excreted in human milk.

5.7.4.3 Capecitabine

Lactating mice given a single oral dose of capecitabine excreted significant amounts of capecitabine metabolites into the milk. It is not known whether capecitabine is excreted in human milk. Subjects receiving capecitabine should not breast-feed.

5.7.4.4 Epirubicin

It is unknown whether epirubicin is excreted in human milk, however other anthracyclines are known to be excreted in breast milk. Subjects receiving epirubicin should not breast-feed.

5.8 Subject Withdrawal/Discontinuation Criteria

Subjects may withdraw consent at any time for any reason or be dropped from the trial at the discretion of the investigator should any untoward effect occur. In addition, a subject may be withdrawn by the investigator or the Sponsor-Investigator if enrollment into the trial is inappropriate, the trial plan is violated, or for administrative and/or other safety reasons. Specific details regarding discontinuation or withdrawal are provided in Section 7.1.4 – Other Procedures.

Even if a subject discontinues trial treatments, they will be encouraged to continue to participate in collection of data regarding the endpoints, including DFS and OS.

A subject must be discontinued from the trial treatments for any of the following reasons:

- The subject or legal representative (such as a parent or legal guardian) withdraws consent.
- Confirmed radiographic disease progression or recurrence
- Unacceptable adverse experiences as described in Section 5.2.1.2
- Intercurrent illness that prevents further administration of treatment
- Investigator's decision to withdraw the subject
- The subject has a confirmed positive serum pregnancy test
- Noncompliance with trial treatment or procedure requirements
- The subject is lost to follow-up
- Completed 12 months of uninterrupted treatment with pembrolizumab following surgical resection or 17 administrations of study medication, whichever is later.

Note: 12 months of study medication is calculated from the date of first dose following surgical resection.

- Administrative reasons

The End of Treatment and Follow-up visit procedures are listed in Section 6.0 (TRIAL FLOW CHART) and Section 7.1.5 (Visit Requirements). After the end of treatment, each subject will be followed for 30 days for adverse event monitoring (serious adverse events will be collected for 90 days after the end of treatment as described in Section 7.2.3.1). Subjects who discontinue for reasons other than progressive disease will have post-treatment follow-up for disease status until disease progression or recurrence, withdrawing consent or becoming lost to follow-up. After documented disease progression each subject will be followed by telephone for overall survival until death, withdrawal of consent, or the end of the study, whichever occurs first.

